11.2 ANALYSIS OF PRIMARY OUTCOME

We will first graphically explore the relationship between responses and dose by time and specify how dose and time will be parameterized. For example, if a linear dose-dependent relationship is shown at each follow-up time (e.g., incremental drop in amygdala reactivity with increasing duration of daily light pulse), we will assess it by including dose (in minutes) and will include the interactions of time by dose to assess how/if the relationship changes over time (e.g., no difference across groups at baseline and dose-dependent relationship at weeks 2 and 4). A test of overall dose response relationship between duration of daily light pulse and reduction from baseline in amygdala reactivity will be established based on the significance of the interaction term. Time can also be included as categorical indicators to see, for example, if 4 weeks, relative to 2 weeks achieve even greater (or no greater) response.

If a nonlinear dose-dependent relationship is shown in graphs, it will be explored using indicators of dose groups. If the relationships at 2 weeks differ from those at 4 weeks, we will analyze them using separate models.

Statistical analysis will be performed using SAS 9.3. Regarding missing data, if "non-ignorable" patterns are detected, then "pattern mixture", "selection models", or other appropriate strategies will be used to examine the impact of the missing data pattern on the key outcomes [108, 109]. All analyses will include tests for sex differences, in order to examine sex as a biological variable.

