Data collection is expected to last approximately 19 months with plans to enroll approximately 3 participants a month with possible exceptions for lower enrollment in November and March when offset and onset of daylight savings time can confound circadian rhythms and normal sleep habits.

6 Study Population

We plan to enroll 66 individuals with a recent history of DSM-5 Criterion A trauma and reported comorbid mood and arousal symptoms (as measured by the DASS questionnaire). These criteria are designed to include a wide variety of people with traumatic stress to maximize generalizability while ensuring that treatment and outcomes measures are not significantly affected by potential confounding variables. Additionally, we believe that this approach will lead to a transdiagnostic sample that shares the common feature of amygdala reactivity [11-14]. Diagnostic information will be collected via the Structured Clinician Interview for DSM Disorders (SCID-5-RV) [57] during Visit 2.

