8.2 Participant Discontinuation or Withdrawal from Study

Reasons why a participant might be withdrawn from the study:

- Participant request
- Any new diagnosis that would be considered part of the original exclusion criteria for this study
- Positive breathalyzer or drug test at the study at Visits 3, 4, 5 or 6
- Start of new treatment or therapy during study period
- Significant study intervention non-compliance, i.e. inability or unwillingness to complete study intervention or outcome assessments
- Any clinical event or other medical condition or situation such that continued participation in the study would not be in the best interest of the subject
- If the participant meets an exclusion criterion (either newly developed or not previously recognized) any time
- Lost-to-follow up

If possible, reasons for withdrawal will be documented. Data from dropouts or withdraws will be retained to minimize data loss.

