9.7 FMRI

Amygdala reactivity will be measured using fMRI and change in BOLD signal measures across the study period. Images will be acquired using an Echo-Planar Imaging sequence (TR=800 ms, FOV=23, slice=2.4mm, 96x96 matrix) to measure brain function at rest and during the EFAT task, optimized to reduce susceptibility artifact. fMRIs (initially at visits 3, 5 and 7 but later changed to only visits 3 and 7) will be scheduled at the North Campus facility and must occur within 7 days of the clinician-administered and self-reported assessments of trauma stress and mood (see Section 9.3)

9.7.1 fMRI Practice

As part of the screening process, individuals will be able to lie in the mock scanner located at the Rachel Upjohn Building. This scanner is built to size, and includes simulating scanner noise from speakers so people can hear the noises associated with scanning.

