11 STATISTICAL CONSIDERATIONS

11.1 GENERAL APPROACH

The objective of this study is to establish a signification dose response relationship between the duration of morning light treatment and reduction in amygdala reactivity from baseline to treatment week 2 (study week 3) and/or treatment week 4 (study week 5).

Statistical analyses will include intent-to-treat and completer analysis. Data will be analyzed using responses at all three times (baseline, 2 [when data available] and 4 weeks) as dependent variables using a mixed-effects longitudinal model [106, 107] with participants as random intercepts to account for between participant variability and time as a predictor.

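### For participants with both scans, the planned dose-by-time test compares raw change in amygdala reactivity; adjusting for the baseline scan would usually be more precise at almost no cost

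*Combined protocol and SAP*

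**What the plan says.** Section 11.1 sets out a mixed model with a random intercept per participant and time as a predictor: "Data will be analyzed using responses at all three times (baseline, 2 [when data available] and 4 weeks) as dependent variables". Section 11.2 adds dose: "we will assess it by including dose (in minutes) and will include the interactions of time by dose". The dose-response finding "will be established based on the significance of the interaction term".

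Section 11.2 allows three variations: time as categories, separate models for weeks 2 and 4, and a change of dose form ("If a nonlinear dose-dependent relationship is shown in graphs, it will be explored using indicators of dose groups"). None of them names baseline reactivity as a covariate or makes the arms share a baseline mean. The words "no difference across groups at baseline and dose-dependent relationship at weeks 2 and 4" illustrate a pattern that the interaction might show; they do not constrain the model.

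Baseline reactivity is not a minimisation variable (Section 7.4.1). Section 11.3.3 names childhood trauma and sleep measures as possible covariates where imbalance calls for them. That list is open, but reactivity is not on it.

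Section 9.7 gives the scan schedule as "initially at visits 3, 5 and 7 but later changed to only visits 3 and 7". Section 6 gives the size: "We plan to enroll 66 individuals".

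**The concern.** The objective in Sections 4 and 11.1.1 is a significant dose response, sought with 66 participants in three arms. Randomisation makes the arms equal at baseline in expectation. The planned model does not use this, because it estimates a separate dose term at baseline. The noise of the baseline scan then passes in full into the change score. An analysis that conditions on the baseline scan removes only as much of it as predicts the follow-up scan, and usually has a smaller standard error. What is at stake is the chance of detecting a real dose response with data the trial already collects.

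**Working it through.** **The plan's own figure.** There is none to reproduce. The documents state 66 participants but no alpha, power, SD, correlation or dropout rate for this test.

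**Is the interaction a raw-change comparison?** The described model was fitted to one simulated data set of 66 with two scans each. The dose-by-time estimate was -0.007111 (SE 0.007811). Regression of week 4 minus baseline on dose gave the same estimate and SE. With dose indicators, the interactions equalled the between-arm contrasts in mean change (-0.0979 and -0.3182).

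The identity needs both scans. Section 8.2 says "Data from dropouts or withdraws will be retained to minimize data loss", so some participants may have a baseline scan only. With 10 week-4 scans removed, the mixed model gave -0.00443 and the change regression -0.00604.

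**Relative precision.** Let s0 and s1 be the baseline and week-4 SDs and rho their correlation.

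- Raw change: residual variance = s0² + s1² - 2·rho·s0·s1
- Baseline as covariate: residual variance = s1²·(1 - rho²)
- Difference = (s0 - rho·s1)², which is never negative

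In large samples adjustment therefore never loses. The two are equal only when rho·s1 = s0. With equal SDs the variance ratio (plan/adjusted) is 2/(1 + rho): 1.54 at rho 0.3, 1.33 at 0.5, 1.11 at 0.8 and 1.05 at 0.9. The lost degree of freedom multiplies the adjusted variance by 1 + 1/(n - 4) = 1 + 1/62, about 1.6%.

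**Power.** All inputs except the total of 66 and the three durations are assumptions: 22 per arm, two-sided 0.05, a linear dose slope, two scans, and a 60-versus-15-minute difference of 0.5 baseline SD.

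- Mean dose = 35 minutes, so Sxx = 22 × (20² + 5² + 25²) = 22 × 1,050 = 23,100
- Slope = 0.5/45 = 0.01111 per minute
- Noncentrality = 0.01111 / sqrt(variance/23,100), with 64 df (change) or 63 df (adjusted)

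Example, rho 0.5 and equal SDs. Plan: variance 1.000, SE 0.00658, noncentrality 1.69, power 38%. Adjusted: variance 0.75 × (1 + 1/62) = 0.762, SE 0.00574, noncentrality 1.93, power 48%.

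| rho | week-4/baseline SD | variance, plan | variance, adjusted | power, plan | power, adjusted |
|---|---|---|---|---|---|
| 0.3 | 1.0 | 1.400 | 0.925 | 29% | 41% |
| 0.5 | 1.0 | 1.000 | 0.762 | 38% | 48% |
| 0.8 | 1.0 | 0.400 | 0.366 | 75% | 78% |
| 0.9 | 1.0 | 0.200 | 0.193 | 96% | 97% |
| 0.6 | 0.8 | 0.680 | 0.416 | 52% | 73% |
| 0.6 | 1.0 | 0.800 | 0.650 | 46% | 54% |
| 0.6 | 1.2 | 1.000 | 0.936 | 38% | 40% |
| 0.6 | 1.5 | 1.450 | 1.463 | 28% | 28% |

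If only 18 per arm have both scans, the figures are 25% v 34% (rho 0.3) and 32% v 40% (rho 0.5).

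**Where adjustment is slightly worse.** Counting the lost degree of freedom, this happens for rho above about 0.97 with equal SDs, 0.75 to 0.89 at SD ratio 1.2, and 0.56 to 0.75 at SD ratio 1.5.

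**The case against.** The strongest reply is that modelling change is a legitimate choice that answers an objective stated as reduction from baseline, and that the benefit cannot be shown from the documents. Both statements are true. At rho 0.8 or 0.9, or with a larger week-4 SD, the gain is small or nil. This limits the weight of the point. It does not remove it, because adjustment estimates the same dose effect and its possible cost is far smaller than its possible gain.

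A second reply is that nothing forbids adjustment: Section 11.2 leaves the parameterisation open and the list in Section 11.3.3 is not closed. That also stands, and the claim is only that no described version adjusts. An option left open is not a specification, and Section 11.3.3 ties adjustment to observed imbalance rather than to prognostic value.

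Third, the decision to proceed does not rest on this test. Section 11.1.2 requires Cohen's d of at least 0.5 with one of the durations, and Section 11.3.1 presents the mixed model as an addition to the effect-size comparison. This stands for the go/no-go decision. Sections 4 and 11.1.1 nevertheless make a significant dose response the objective.

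Fourth, the two-scan figures may not describe every participant. The week-2 scan was dropped in version 13.0, and the documents do not say how many had been scanned at week 2 by then. This also stands, and the figures should not be carried over to those participants.

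**Conclusion.** The point holds as a cheap improvement to consider, not as an error. For participants with baseline and week-4 scans the planned test is a comparison of raw change, and no described version uses baseline reactivity to sharpen it. Under the assumptions above the power gain runs from about 20 points to none. The actual gain is unknown, because the correlation, SDs, alpha and effect are not in the documents.

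A reader might infer more than this:

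- **That the test is biased or has the wrong error rate.** For a dose form fixed in advance it does not. In null simulations (rho 0.3 to 0.8, SD ratio 0.8 to 1.5) the change score and the covariate model both rejected in 4.9% to 5.1% of trials. Choosing the dose form after viewing graphs is a separate issue.
- **That the trial is underpowered by a known amount.** The power figures rest on assumed inputs and show only the range.
- **That the go/no-go decision is compromised.** That rule is about effect size and does not use this test.

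**What to change.** Before data are viewed, specify the dose-response analysis as follow-up amygdala reactivity (week 4, plus week 2 where available) on dose, with baseline reactivity as a covariate.

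A regression on week 4 alone would drop retained participants who lack that scan, which sits uneasily with the intent-to-treat analysis promised in Section 11.1. To keep them, use instead a longitudinal model with a common baseline mean across arms, unstructured covariance across visits and a small-sample degrees-of-freedom correction such as Kenward-Roger. Without a correction, simulated type I error for that model was 5.7% to 5.9% with a normal reference and 5.3% to 5.4% with t on 64 df. Kenward-Roger itself was not simulated.

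Do not simply drop the dose main effect from the random-intercept model. That model forces equal variances across visits, and its simulated type I error was 2.6% to 3.2% at SD ratio 0.8 and 9.1% to 9.7% at 1.5.

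The cost is a short change to the model specification, with no new data or participants. The covariate uses one degree of freedom (about 1.6% of variance with 66 participants) and is slightly worse than the plan in the narrow ranges given above. The SPM12 second-level analyses in Section 11.3.1, which are meant to mirror the extracted-value model, need the same covariate.

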11.3 EXPLORATORY ANALYSES

11.3.1 fMRI

In addition to the effect size comparison for the ROI analysis, we will analyze the data with the mixed-effects longitudinal regression model described above. We will also conduct exploratory whole-brain voxel-wise analyses, employing a similar statistical approach across the entire brain in an exploratory search to generate hypotheses for subsequent study. Statistical maps for the whole brain analysis will be created using a threshold of p<0.001 with a cluster threshold of at least 10 voxels. Brain images will be entered into second-level analyses implemented in SPM12 to mirror analyses performed with extracted values. We will also conduct exploratory amygdala analyses to evaluate: 1) different sub-regions within the amygdala; 2) activation outside of amygdala using whole-brain voxel-wise analyses; and 3) using amygdala circuit seeds for functional (psychophysiological interaction analyses) [110], resting state [111, 112] and effective (dynamic causal modeling) connectivity analyses [113].

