4 OBJECTIVES & ENDPOINTS

This study is a part of a larger proposal under the NIH R61/R33 mechanism which requires specific Go-No Go Criteria to transition between the two phases of the proposal. This protocol is specific to the R61 Phase. The specific aim and **objective for this phase** (i.e. study) is to **establish a significant dose response relationship between duration of morning light pulse and reduction in amygdala reactivity** from baseline to week 2 and/or week 4.

The **endpoint is whole-brain oxygen-level-dependent (BOLD) fMRI signal** using a priori regions of interest **specific to the bilateral amygdala**.

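### The exploratory whole-brain rule (p<0.001, at least 10 voxels), read as uncorrected, does not control the chance of false clusters

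*Combined protocol and SAP*

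**What the plan says.** Section 11.3.1 plans "exploratory whole-brain voxel-wise analyses, employing a similar statistical approach across the entire brain", described as carried out "in an exploratory search to generate hypotheses for subsequent study". The display rule is: "Statistical maps for the whole brain analysis will be created using a threshold of p<0.001 with a cluster threshold of at least 10 voxels". The software is also named: "Brain images will be entered into second-level analyses implemented in SPM12 to mirror analyses performed with extracted values".

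The section mentions no family-wise or false-discovery correction, cluster-level p value, permutation test, or extent derived from estimated smoothness. It does not label p<0.001 as corrected or uncorrected. Section 9.7 gives the acquisition settings ("TR=800 ms, FOV=23, slice=2.4mm, 96x96 matrix"), but no smoothing kernel, resampled voxel size or brain mask volume is stated.

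The primary endpoint in section 4 is defined "using a priori regions of interest" in the bilateral amygdala. The go/no-go rule in section 11.1.2 is a Cohen's d for amygdala reactivity. Neither uses the whole-brain threshold.

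**The concern.** An extent threshold limits false clusters only if it is set from how large noise clusters tend to be. That depends on how smooth the map is, how big a voxel is, and how much volume is searched. A flat count of 10 uses none of these, so the same rule can be lax on one processing choice and strict on another. A reader of a map thresholded this way cannot say what error rate it carries.

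The stake is limited but real. The search exists to produce hypotheses, and a rule that often returns clusters from noise alone is a weak filter for them. Saying which clusters also pass a proper cluster-level criterion would let readers weigh them.

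**Working it through.** The plan states no error rate for the whole-brain maps, so there is no figure to reproduce. The check asks how often a map with no true effect shows at least one qualifying cluster.

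**Inputs from the documents**
- Threshold p<0.001 and extent of at least 10 voxels (section 11.3.1).
- Acquired voxel: reading the field of view as 23 cm, 230 mm / 96 = 2.396 mm in plane, with a 2.4 mm slice (section 9.7).
- Sample: "We plan to enroll 66 individuals" (section 6), so about 66 − 2 = 64 degrees of freedom for a dose slope on change maps, before dropout.

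**Assumptions, because the documents are silent**
- p<0.001 is uncorrected and one-sided, so u = 3.09.
- Search volume V is 1.4 to 1.5 litres, with 1.2 to 1.8 litres as a wider range.
- Analysis voxel is 2, 2.4 or 3 mm.
- Smoothness (FWHM) is 6 to 15 mm, with about 5 mm as a low case.

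**Formulas (Gaussian random field, three dimensions)**
- Expected clusters: E[m] = (V/FWHM³) (4 ln 2)^1.5 (2π)^−2 (u² − 1) exp(−u²/2). The constants give 4.617 × 0.02533 × 0.07216 = 0.00844, so E[m] = 0.00844 V/FWHM³.
- Expected voxels above threshold: E[N] = 0.001 × number of voxels.
- β = (Γ(2.5) E[m]/E[N])^(2/3), with Γ(2.5) = 1.329.
- P(size ≥ 10) = exp(−β × 10^(2/3)) = exp(−4.642 β).
- P(at least one) = 1 − exp(−E[m] × P(size ≥ 10)).

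**Worked cases at V = 1.5 litres**
- 2.4 mm voxels, 8 mm: E[m] = 0.00844 × 1,500,000/512 = 24.7; E[N] = 108.5; β = 0.451; P(size ≥ 10) = 0.123; 24.7 × 0.123 = 3.05 clusters expected; P = 95%.
- 2.4 mm voxels, 6 mm: E[m] = 58.6; β = 0.802; P(size ≥ 10) = 0.0242; 1.42 clusters expected; P = 76%.
- 3 mm voxels, 6 mm: E[m] = 58.6; E[N] = 55.6; β = 1.253; P(size ≥ 10) = 0.0030; 0.175 clusters expected; P = 16%.

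**Results, one-sided, 1.5 litres unless stated**

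| Voxel | FWHM | Theory | Simulation |
|---|---|---|---|
| 2.4 mm | 4.8 mm | 29% | 19% |
| 2.4 mm | 5 mm | 38% (36% at 1.4 l) | 29% (1.4 l) |
| 2.4 mm | 6 mm | 76% (73% at 1.4 l) | 74% (71% at 1.4 l) |
| 2.4 mm | 8 mm | 95% (94% at 1.4 l) | 94% (97% at 1.4 l) |
| 2.4 mm | 10 mm | 96% (95% at 1.4 l) | 98% (98% at 1.4 l) |
| 3 mm | 6 mm | 16% (13-19% over 1.2-1.8 l) | 14% |
| 3 mm | 8 mm | 61% | 67% |
| 3 mm | 10 mm | 79% | 83% |

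The 1.5-litre simulations used 40 to 100 noise fields per setting (18-neighbour clusters). The 1.4-litre ones used 300 (26-neighbour clusters). A simulated 64-df t-map of the dose slope with 2.4 mm voxels at 8 mm gave 98% in 29 maps. At 2 mm voxels theory gives 86% to above 99% over 6 to 15 mm and 1.2 to 1.8 litres.

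Less smooth maps on coarse voxels go the other way. At 3 mm voxels and 5 mm FWHM, E[m] = 101.3, β = 1.804 and P(size ≥ 10) = 0.00023, so P is about 2%. The theory is rough at under two voxels of smoothness, but the direction is clear: the rule can fall below 5% as well as far above it.

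**Extent that would give 5%.** Setting E[m] exp(−β k^(2/3)) = −ln 0.95 = 0.0513 at 1.5 litres and 2.4 mm voxels gives k of about 27, 51, 84, 124 and 194 voxels for FWHM 6, 8, 10, 12 and 15 mm.

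These are chances for one map in one direction. Reading both directions raises them (from 76% to 94% at 2.4 mm voxels and 6 mm).

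**The case against.** The strongest reply is that the analysis is openly exploratory. It sits under that heading, is described as a search for hypotheses, and is never said to control error or to turn clusters into findings. With 66 participants over three arms, a stricter threshold costs sensitivity, and how strict to be in such a search is partly a matter of preference. The plan also does not say that corrected values will be withheld, and SPM12 can supply them. All of this stands, and it keeps the point minor. It does not supply an error rate, and the text leaves open even whether p<0.001 is corrected.

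A reader might infer that regions taken into the next phase of the programme would often be noise. The documents do not support that. The transition rests on the amygdala effect size in section 11.1.2, and nothing says that whole-brain clusters select later targets. Nor does the calculation give the share of reported clusters that are noise, since that also depends on how many true effects exist, which is unknown.

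A reader might also infer that a null map will usually show a cluster whatever the processing. That fails when smoothness is about two voxels or less, as the 4.8-5 mm rows and the 3 mm row at 6 mm show.

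**Conclusion.** The point holds as a minor, conditional one. Read as an uncorrected voxel threshold, the rule leaves the cluster-level false-positive rate uncontrolled: over plausible settings it runs from a few per cent to near certainty. It exceeds one half at 2 or 2.4 mm voxels with smoothness of 6 mm or more, and at 3 mm voxels with 8 mm or more.

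This rests on assumed brain volume, analysis voxel size and smoothness, on one-sided maps, and on the uncorrected reading. If p<0.001 were meant as family-wise corrected, the concern would fall away; pairing it with a fixed extent makes that less likely, but the text should say. The consequence is confined to how much weight hypotheses from the whole-brain search can bear.

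**What to change.** Amend section 11.3.1 to:
- state that p<0.001 is the uncorrected cluster-forming threshold;
- report the SPM12 cluster-level family-wise p value for every cluster shown;
- call a whole-brain cluster a finding only at cluster-level family-wise p<0.05;
- list the remaining clusters of at least 10 voxels separately, labelled uncorrected and hypothesis-generating.

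Reporting the estimated smoothness, analysis voxel size and search volume with the maps would let readers judge the extent for themselves.

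This needs no new data and no software beyond what the plan names, and no exploratory result is suppressed. The downside is that fewer clusters are called findings.

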11.3.2 Traumatic stress symptoms

We will also examine the clinician-administered (PSSI-5, HAM-D, HAM-A) and self-report measures (DASS, PCL-5) of traumatic stress symptoms with a mixed-effects longitudinal regression model as described above.

